5.5.1 Reasons for Withdrawal

Participants are free to withdraw from participation in the study at any time, for any reason, with no explanation upon request. This decision will not interfere or alter in any way their following treatments and pain management if they are patients of the dental school, the Brotman Facial Pain Clinic or the Oral and Maxillofacial Surgery Clinic.

If a participant does not return for a scheduled visit, every effort will be made to contact the participant and to document the outcome. If a participant withdraws consent and refuses to come to an Early Termination Visit, no further evaluations will be performed, and no attempts will be made to collect additional data.

Investigators may withdraw a participant for any of the following reasons:

- Withdrawal of consent
- The participant does not meet eligibility criteria for randomization.
- Any clinical adverse event (AE), laboratory abnormality, or other medical condition or situation occurs such that continued participation in the study would not be in the best interest of the participant.
- The subject meets an exclusion criterion (either newly developed or not previously recognized) that precludes further study participation.
- Pregnancy
- At Investigator discretion

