5.5.2 Handling of Subject Withdrawals or Subject Discontinuation of Study Intervention

Participants withdrawn after randomization will not be replaced. Participants who are withdrawn voluntarily or by the investigator will be discontinued from the study.

Study staff will complete a study disposition form in the eCRF, indicating the reason for discontinuation.

If the patient is a patient from the school and/or is interested in following TMD care at the Brotman Facial Pain clinic, will be referred to the faculty practice clinic front desk for information and to schedule an appointment if wants to.

Unblinding, if required, will be carried out according to the procedures described in

Section 5.4.2. A participant who has an AE at the time of discontinuation will be followed until the event returns to baseline, resolves, or is stabilized. If the AE does not meet one of these outcomes within 30 days after discontinuation or the end of the study, the participant will be referred to an appropriate provider for continued medical care (See section 9.2).

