6.3 Modification of Study Product Administration for a Subject

If a dose of Erenumab is missed, will be administered as soon as possible. Thereafter, Erenumab will be scheduled monthly from the date of the last dose.

The safety profile of erenumab has been favorable in clinical trials and in the post-marketing setting. A limited number of adverse drug reactions (injection site reactions, constipation, muscle spasm, and pruritus) have been identified at low frequencies (< 5%) in clinical trials. In the long-term use of erenumab, the safety profile remained consistent through 5 years of open-label treatment. In post-marketing settings, hypersensitivity reactions (including rash, angioedema and anaphylactoid reactions) and constipation with serious complications have been reported. In addition, oral sores (eg, stomatitis, mouth ulceration, oral mucosal blistering), alopecia and rash (eg, rash papular, exfoliative rash, rash erythematous, urticaria, blister) have been observed in post-marketing surveillance.

Hypertension or worsening of high blood pressure can happen after receiving Erenumab. Hypertension is in our exclusion criteria, however if a new onset of hypertension occurs, the participant will be withdrawn of the study and will be the participant will be referred to an appropriate practitioner for continued care (see section 9.2).

Participants will be closely monitored for any of these AEs, during the clinic visit and between visits by telephone. Potential risks and discomforts will be clearly stated in the ICF. Exclusion criteria includes medical history of constipation or taking medications associated with decrease of G.I motility as well as pre-existent hypertension (See 5.2). If the participant reports a hypersensitivity reaction (rash, angioedema, anaphylaxis), new onset constipation or new onset of hypertension or any of the reactions described above, if there is worsening of TMD signs and symptoms during the 18 weeks of participation or if the participant decides against using Erenumab, he/she will be discontinued from the study (See 2.3.1 and 5.5.2).

The following expected events will not be considered reportable AEs:

- Temporary injection site reactions such as pain, erythema, pruritus after the injection of Erenumab
- Minor bleeding or bruising resulting from the blood draw
- Temporary pain or temporary increases in existing pain prompted during the TMD clinical examination or PPT.

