During the course of the study, participants will not be restricted in the use of non-pharmacological therapies, with the exception of acupuncture, physical therapy and splint therapy. If a participant starts these therapies for the management of pain during the study, the use of these therapies will be recorded in the eCRF and the patient will need to be withdrawn of the study. The use of intraoral appliances at night only is allowed if was started at least 30 days prior to Screening and Baseline V0.

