The Pressure Pain Threshold (PPT) will be defined as the amount of pressure at which the participant first perceives pressure to be painful. The PPT measurements will be performed by trained staff using a pressure algometer (Wagner, Greenwich, CT). Calibrated pressured will applied bilaterally over the masseter, temporalis, upper trapezius, the TMJs, and the lateral epicondyles. One pre-trial assessment will be performed at each anatomic structure followed by additional assessments until 2 measures differing by less than 0.2 kg are obtained, or 5 assessments are administered. In either case, the mean of the 2 closest values will be recorded as the threshold estimate. Pressure stimuli will be delivered at an approximate rate of 1 kg/s. The cutoff pressure for all sites will be 5 kg. The values from the right and left sides will be averaged to obtain a single PPT value per anatomical site [34, 35].

- **Daily Symptom Diary**

Participants will be asked to complete the Daily Symptom Diary at the end of each day during the baseline phase and during the study (visits 1-5).

Participants should have at least 80 % compliance with the DSD.

The diary collects the participant's pain intensity (reported on a 0-100 numeric rating scale) and duration (reported on a 0-100 percentage scale), pain days and use of pain medication. Participants are required to complete a Daily Symptom Diary electronically or on paper and a new form will be used for each month of the study. These forms may be returned in person at study visits.

Outcome Measure Questionnaires

Listed in the Schedule of Events (Appendix A). Questionnaire forms on paper will be provided to the participants if an electronic form is not feasible.

Some questionnaires are self-administered, and others will be administered by trained study staff.

- Jaw Functional Limitation Scale. This is a 20-item instrument that measures limitations across 3 domains related to TMJ biomechanics: masticatory function (6 items), vertical jaw mobility/jaw opening (4 items), and verbal and emotional expression (8 items). Two items are not scored as part of these 3 subscales. A degree of limitation is rated on a 0-10 scale from 0 ("no limitation") to 10 ("severe limitation") [36, 37].
- Oral Behaviors Checklist (OBC). Evaluates parafunctional behaviors and generates a single scale representing the frequency of 21 activities such as clenching, chewing gum, and holding objects between teeth, yawn [38, 39].

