9 ASSESSMENT OF SAFETY

9.1 Specification of Safety Parameters

This study involves the use of Erenumab, a fully human monoclonal antibody that is a CGRP receptor antagonist FDA approved for the prevention of migraine in adults

The participants of this study will be closely monitored and follow up in their clinic visits and between visits with telephone calls. As part of the study outcomes, the study staff will record information regarding AEs. Overall health parameters will be captured on case report forms. These will be completed at every visit and data will be compiled for review by the IRB.

The description of potential risks is described in 2.3 and 6.3. The most common side effects of the use of Erenumab are:

- Injection site reactions: which may include tenderness, pain, redness, itching, bruising, firmness, or hypersensitivity
- Constipation
- Muscle spasms/cramps
- Itching (pruritus)

Allergic reactions can happen within hours to days after using erenumab. Therefore, after the injection is administered, the participant will wait in the room for 20 minutes and the evening of the treatment visit, the participant will receive a follow up phone call and the information will be recorded.

If the participant reports a hypersensitivity reaction (rash, angioedema, anaphylaxis), new onset constipation or new onset of hypertension or any of the reactions described above, if there is worsening of TMD signs and symptoms during the 18 weeks of participation or if the participant decides against using Erenumab, he/she will be discontinued from the study (See 2.3.1 and 5.5.2).

The following expected events will not be considered reportable AEs:

- Temporary injection site reactions such as pain, erythema, pruritus after the injection of Erenumab
- Minor bleeding or bruising resulting from the blood draw
- Temporary pain or temporary increases in existing pain prompted during the TMD clinical examination or PPT.

9.1.1 *Unanticipated Problems*

The Office for Human Research Protections (OHRP) considers unanticipated problems involving risks to subjects or others to include, in general, any incident, experience, or outcome that meets **all** of the following criteria:

- Unexpected in terms of nature, severity, or frequency given (a) the research procedures that are described in the protocol-related documents, such as the IRB-approved research protocol and informed consent document; and (b) the characteristics of the subject population being studied;

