12.2 Sample Size Considerations

The proposed sample size of 60 randomized patients split into two independent groups is based on a 30-50% reduction in TMD pain scores at follow-up, assuming a power of 90%, alpha = 0.05, assuming a 0.5 (medium) effect size. This was calculated using GPower software. This sample size is also based on the conservative assumption of a 15% patient drop out at follow up.

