12.4 Final Analysis Plan

The main goal of the statistical analyses is to estimate change in study primary and secondary endpoints to evaluate efficacy of Erenumab. Intention to treat analysis will be performed using a within-subjects student's pair t-test or repeated measures ANOVA (if more than two time points) to determine significant reduction in pain after drug intervention in each patient. Subsequently, a between-subjects unpaired t-test or two-way mixed designed ANOVA (if more than two time points) will be performed to determine difference between the placebo and erenumab groups. *Post-hoc analysis* will only be conducted following a significant ANOVA test, to protect from Type I errors. We will use a 2-way between subject's repeated measure ANOVA design to determine difference between the Erenumab group and placebo group, or a between-subjects unpaired t-test if two groups only. We will also use student's paired t-test to determine time points of significance. 50% reduction in pain days will be determined as a function of baseline pain days. Where, appropriate similar statistical procedures will be used for secondary endpoints.

Descriptive statistics for safety measures will also be calculated.

We will collect the following data for descriptive purposes and, if necessary, to use as covariates: Demographic information (age and race/ethnicity), rescue medication history, psychological factors and perceived change in overall status (PGIC).

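### Participants whose TMD worsens, or who decide against erenumab, leave the study and not only the injections, so the month-3 diary score behind the intention-to-treat comparison can be lost for outcome-related reasons

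*Combined protocol and SAP*

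**What the plan says.** Sections 6.3 and 9.1 carry the same rule. A participant leaves the study "if there is worsening of TMD signs and symptoms during the 18 weeks of participation", and also "if the participant decides against using Erenumab, he/she will be discontinued from the study". No threshold for worsening is given. Section 5.5.2 repeats the consequence, "Participants who are withdrawn voluntarily or by the investigator will be discontinued from the study", allows no replacement, and describes follow-up afterwards only for adverse events. Under section 6.6.4, if a participant starts acupuncture, physical therapy or splint therapy for pain, "the use of these therapies will be recorded in the eCRF and the patient will need to be withdrawn of the study".

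Section 8.1 asks participants to "complete the Daily Symptom Diary at the end of each day during the baseline phase and during the study (visits 1-5"). Section 7.5 plans one early-termination visit with the Visit 4 procedures, which include diary review (section 7.3.4).

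The primary endpoint is not described in one way. Section 12.3.2 uses the month before Visit 4. The Précis describes a mean of daily scores over 12 weeks. Section 3.2.1 scores each month, section 4 refers to the 12-week treatment period, and section 12.1 to Visit 1 to Visit 4. Section 3.2.1 calculates a monthly score only with at least 80% diary compliance.

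Section 12.4 says "Intention to treat analysis will be performed", by t-tests or ANOVA, and names no method for missing scores. Section 12.2 adds: "This sample size is also based on the conservative assumption of a 15% patient drop out at follow up".

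**The concern.** An intention-to-treat comparison needs outcomes on everyone randomised, including those who stop treatment. Here, stopping treatment and leaving the study are one event, and one trigger for it, worsening TMD, is close to the outcome itself. Starting another pain therapy is plausibly driven by pain too.

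If erenumab works and worsening drives exit, more placebo patients leave. The placebo patients who stay look better than the whole arm was, and a true effect is understated. With no effect and equal exit there is no bias. If exit differs by arm for other reasons, such as side effects, the bias can go either way. A statistical model can repair part of this later, but not where the diary days that would show the worsening were never recorded.

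**Working it through.** **Plan's own figures.** 15% of 60 is 9, leaving 51. The effect size of 0.5 is matched below by a 10-point difference with SD 20. The stated 90% power does not reproduce: with 30 per arm, two-sided 5%, the noncentral t gives 0.478 without any loss. That is a separate matter, but it is the baseline for the power figures here.

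**When a month-3 score is lost.** Month 3 is days 57 to 84. 80% of 28 is 22.4, so 23 diary days are needed, and 57 + 22 = 79. A diary that stops before about day 79 gives no month-3 score.

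**Bias identity.** Let d be the fraction missing in an arm (0 placebo, 1 erenumab) and D the mean change in those missing minus the mean change in those observed. Then full difference (erenumab minus placebo) = observed difference + d1·D1 − d0·D0.
- 15% missing in each arm with D = 20 in both: 3 − 3 = 0, no bias.
- 15% missing in each arm, D0 = 20, D1 = 0: 0 − 3 = −3, so the benefit is understated by 3 points.
- 10% placebo and 20% erenumab missing, D = 20 in both: 4 − 2 = +2, so the benefit is overstated by 2 points.

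**Simulation (all inputs assumed except the 15%).** Three monthly change scores per patient, SD 20, means −10 placebo and −20 erenumab in each month, correlation 0.5, 0.7 or 0.9. Worsening is a monthly mean change above 0, +10 or +20; probability of exit on worsening 0.25, 0.5, 0.75 or 1. That gives 36 scenarios with 1,000,000 patients per arm. Leavers are assumed to keep the drug benefit. In 25 scenarios the average loss is at or below 15%; in 14 it is at or below 7.5%, which represents worsening causing half of all dropout. Differences in points (truth 10), with range ends good to about 0.1:

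| Endpoint; timing of exit | Loss up to 15% | Loss up to 7.5% |
|---|---|---|
| Month 3, those remaining; after the worsening month is scored | 6.8–9.6 | 8.1–9.6 |
| Month 3, those remaining; before that month is scored | 6.6–9.4 | 7.9–9.4 |
| 12-week average of available months; after | 10.0–10.6 | 10.0–10.4 |
| 12-week average of available months; before | 9.5–10.0 | 9.6–10.0 |

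The 6.8 comes from one corner: correlation 0.9, threshold +10, certain exit, losses of 20.2% placebo and 9.0% erenumab. Those remaining change by −16.48 and −23.28, and 23.28 − 16.48 = 6.80.

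**Power**, loss up to 15%, exit after scoring: 0.29–0.45, against 0.42–0.47 if the same loss were random.

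**Likelihood model using all monthly scores**, loss up to 15%: 9.9–10.0 when the worsening month is scored before exit, 8.0–9.9 when it is not.

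**No true effect.** Equal exit: no bias, false-positive rate 5.0%. An extra 10% of erenumab patients leaving from those with above-median pain: spurious benefit of 0.9–1.6 points, false-positive rate 5.4–6.1%.

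**If benefit is fully lost off drug**, the intention-to-treat target is itself 10 − 10 × erenumab loss. With losses of 1.1% to 9.0% that is 9.9 to 9.1.

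**The case against.** The strongest reply is that the size depends on one endpoint definition among several. Averaging each patient's available months, one reading of the Précis and section 4, leaves little bias. This stands, and the figures must be read as conditional on section 12.3.2.

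Second, 15% is total dropout. Side effects, pregnancy and voluntary withdrawal share it, so worsening is unlikely to fill it alone. This stands too; hence the column for half.

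Third, worsening in sections 6.3 and 9.1 is undefined and apparently clinical. Modelling it as a threshold on the diary mean ties exit closely to the endpoint. That is an assumption, and a looser link would give less bias.

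Fourth, section 12.4 does not say that incomplete patients are dropped, and a separate SAP is listed under Supplemental Materials but was not available. It may name a method. It cannot recover diary days never collected.

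Fifth, the early-termination visit can capture diary entries up to exit. It cannot supply later days of month 3.

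A reader might also infer that the protocol orders diary collection to stop at discontinuation. No sentence does so. The one explicit clause, "no further evaluations will be performed, and no attempts will be made to collect additional data", covers participants who withdraw consent and refuse the early-termination visit. What the text shows is the absence of any provision for continuing.

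**Conclusion.** The concern holds as a cheap improvement. The plan removes participants from the study for reasons tied to the outcome and has no provision for keeping the diary going afterwards. Under the endpoint in section 12.3.2 it can therefore lose month-3 scores that the promised analysis needs.

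The size is an illustration. It rests on SD 20, a 10-point effect, an assumed threshold for worsening, and a month-3 analysis of those with a score. On those terms, with exit after the worsening month is scored, a 10-point effect appears as 6.8 to 9.6 if worsening fills the whole 15%, and about 8.1 to 9.6 if it fills half. With a 12-week average of available months it stays within about 0.6 points of the truth.

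A reader might infer that the trial will miss a third of the effect, or that it favours erenumab. The documents support neither. The first is a single corner of an assumed grid. The second needs exit to differ by arm, and the documents give no exit rates by arm.

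**What to change.** 1. Leave unchanged who stops treatment. Reconcile sections 5.5.2, 6.3, 6.6.4 and 9.1 with 12.4 by separating stopping study drug from stopping data collection. Ask participants who have not withdrawn consent to continue the existing diary, electronic or paper, to Visit 4. Provide a return route for paper forms, since section 8.1 has them handed in at visits that these participants may no longer attend. This step matters most, because modelling alone recovers only 8.0 to 9.9 of 10 points when patients leave before the worsening month is scored.
2. In section 12.4, analyse all randomised participants with a likelihood-based repeated-measures model that uses every available monthly score and has baseline in the model. State how those with no post-baseline monthly score are handled, such as anyone leaving before 23 diary days in month 1.
3. Add one sensitivity analysis with unfavourable values after withdrawal for worsening. The size of the shift is the sponsor's choice.
4. Choose one primary endpoint definition and make the Précis and sections 3.2.1, 4, 12.1 and 12.3.2 agree with it.
5. Separately, reconcile the early-termination column of Appendix A with section 7.5. As extracted, that column has no mark for diary collection, TMD examination, pressure pain thresholds or blood draw. Check this against the original table.

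Cost: a short amendment with IRB approval (section 15.2), possibly revised consent wording, and diary reminders and form returns for about 9 patients or fewer. The trade-off is that if benefit fades off drug, the estimated effect will be somewhat smaller, 9.1 to 9.9 in the illustration. That is the intention-to-treat quantity.

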9.2 Time Period and Frequency for Event Assessment and Follow-Up

Unanticipated problems will be recorded in the data collection system throughout the study.

The PI and staff personnel will record all reportable events with start dates occurring any time after informed consent is obtained until 30 days after the last day of study participation. At each study visit, the study staff will inquire about the occurrence of AE/SAEs since the last visit. Events will be followed for outcome information until resolution, returns to baseline or stabilizes. If the AE does not meet these outcomes within 30 days after discontinuation of Erenumab or the end of the study, the participant will be referred to an appropriate practitioner for continued care.

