4 STUDY DESIGN

60 patients (30 per each arm) aged 18-65 years old of either sex, and any race or ethnicity presenting chronic painful temporomandibular disorders (TMD) will be randomly assigned in a 1:1 parallel, double-blind, phase 2 single center clinical trial, to receive either Erenumab or placebo. Participants will attend 6 clinic visits (Visit 0-Visit 5) over a period of 21 weeks. The study should be completed over a period of 3 years, with an estimated duration of recruitment of 2.5 years.

Participants will be pre-screened in person at the Brotman Facial Pain clinic, the Oral and Maxillofacial Surgery Clinic both at the University of Maryland, School of Dentistry or by telephone. Potentially eligible and interested participants will be scheduled for a Screening and Baseline Visit (Visit 0). During Visit 0, participants will provide informed consent and be evaluated for eligibility; information including demographics, medical history, concomitant medications, and therapies will be collected. In addition, participants will be assessed for pain level, pain symptoms, jaw function, health status, among other measures and a blood sample will be collected. Procedures will include clinical examinations and tests and the dispensation of various questionnaires, all of which are listed in the Schedule of Events (Appendix A).

Participants who show compliance with the Daily Symptom Diary of at least 80% and who meet the pain score (inclusion criteria) for 28 days/4 weeks (baseline period) after Visit 0, will be randomly assigned to one of two groups (Erenumab or placebo) and will be scheduled for Visit 1 within a week of randomization.

At Visit 1, randomized participants will receive the 1st cycle of management and begin a 12-week drug treatment/placebo phase that will be divided into once a month injection/cycle for a total of 3 cycles. During that period, Visits 2-4 will take place, and many of the baseline assessments will be repeated. Between visits, communication will be conducted by telephone. The final study visit, visit 5, will occur 4 weeks after the last assessment (visit 4) and 8 weeks after the last dosage of drug treatment (Visit 3).

The primary endpoint will be the change in a monthly mean pain intensity score derived from the Daily Symptom Diary. Efficacy will be evaluated as the difference between Erenumab arm and the placebo arm in the monthly pain intensity score (on a 0-100 scale) during the 12 week treatment period.

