7.3.2 Visit 2, 2nd treatment/cycle (Day 28/ 4 weeks after Visit 1)

- Review Daily Symptom Diaries in eCRF or collect and review it in paper forms
- Assess compliance with Daily Symptom Diaries
- Review medical history
- Record concomitant medications and therapies
- Take blood pressure and collect weight
- Administer the Symptom Inventory
- Assess and record adverse events (AEs)
- Perform TMD examination
- Perform Pressure Pain examination
- Perform urine pregnancy test (in women of childbearing potential)
- Review 6 questionnaires from Visit 1 in eCRF or collect and review the paper forms
- Provide instruction to complete 6 new outcome measure questionnaires in paper or electronically for review at Visit 3.

- Provide instruction to complete Daily Symptom Diaries electronically or provide them in paper forms
- Deliver the injection of the study drug or placebo
- Schedule next visit

7.3.3 Visit 3, 3rd and final treatment cycle (Day 56/ after 4 weeks from Visit 2)

- Review Daily Symptom Diaries in eCRF or collect and review it in paper forms
- Assess compliance with Daily Symptom Diaries
- Review medical history
- Record concomitant medications and therapies
- Take blood pressure and collect weight
- Administer the Symptom Inventory
- Assess and record adverse events (AEs)
- Perform TMD examination
- Perform Pressure Pain examination
- Perform urine pregnancy test (in women of childbearing potential)
- Review 5 questionnaires from Visit 2 in eCRF or collect and review the paper forms
- Provide instruction to complete 6 new outcome measure questionnaires in paper or electronically for review at Visit 4.
- Provide instruction to complete Daily Symptom Diaries electronically or provide them in paper forms
- Deliver the injection of the study drug or placebo
- Schedule next visit

7.3.4 Visit 4, assessment of last treatment cycle (Day 84/4 weeks after Visit 3)

- Review Daily Symptom Diaries in eCRF or collect and review it in paper forms
- Assess compliance with Daily Symptom Diaries
- Review medical history
- Record concomitant medications and therapies
- Take blood pressure and collect weight
- Administer the Symptom Inventory
- Assess and record adverse events (AEs)
- Perform TMD examination
- Perform Pressure Pain examination
- Collect blood for Cytokine release assay
- Perform urine pregnancy test (in women of childbearing potential)
- Review 5 questionnaires from Visit 3 in eCRF or collect and review the paper forms
- Schedule next visit

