- Administer the <intervention>.
- Record subject's compliance with <intervention>.
- Following administration of <intervention>
 - Assess vital signs
 - Administer Symptoms Questionnaire

7.4 Follow up and final Study Visit, Visit 5 (Day 112/ 4 weeks after Visit 4)

- Review Daily Symptom Diaries in eCRF or collect and review it in paper forms
- Assess compliance with Daily Symptom Diaries
- Review medical history
- Record concomitant medications and therapies

- Take blood pressure and collect weight
- Administer the Symptom Inventory
- Assess and record adverse events (AEs)
- Perform TMD examination
- Perform Pressure Pain examination
- Perform urine pregnancy test (in women of childbearing potential)
- Review 5 questionnaires from Visit 4 in eCRF or collect and review the paper forms
- Provide final instructions to subject (in case of AE showing later)
- Complete a disposition form

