7.5 Withdrawal Visit

An early termination visit will be performed if a participant is suspended before the completion of the study, prior to withdrawal of consent and with the participant's permission. This could happen during a scheduled or unscheduled visit. The investigator, study coordinator or research staff will discuss with the participant to contact the research team in case AE arise after the withdrawal visit. The assessment and procedures of Visit 4 will be conducted at this visit.

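### New adverse events are to be recorded for 30 days after participation ends, but no contact is scheduled in that period, and anyone who leaves early has a shorter post-dose window than a completer

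*Combined protocol and SAP*

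**What the plan says.** Section 9.2 sets the period for recording reportable events as "occurring any time after informed consent is obtained until 30 days after the last day of study participation". Active enquiry is tied to visits: in 9.2 staff ask at each study visit, and 6.5 and 9.1 add telephone calls between visits and on the evening of an injection.

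Once visits end, the text passes the initiative to the participant. At Visit 5 (7.4) the participant receives final instructions in case an event appears later. At the withdrawal visit (7.5) staff "will discuss with the participant to contact the research team in case AE arise after the withdrawal visit". Appendix A has no column after Visit 5 and early termination.

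The protocol has no status of being off treatment but still in the study. Section 5.5.2 says: "Participants who are withdrawn voluntarily or by the investigator will be discontinued from the study". Sections 6.3 and 9.1 discontinue a participant from the study for hypersensitivity, new constipation, new hypertension or other listed reactions, and also for worsening TMD or a decision against the drug. Section 6.6.4 adds withdrawal for starting acupuncture, physical therapy or splint therapy.

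Section 9.2 also has a second clock: an unresolved event leads to referral if it has not settled "within 30 days after discontinuation of Erenumab or the end of the study".

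**The concern.** A recording window yields data only if someone asks. Here the last 30 days of every participant's window rely on unprompted reports. Because the window runs from the end of participation and not from the last injection, its post-dose length also depends on when the participant leaves. Two participants given the same number of injections can be observed for very different times after the last one.

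At stake is how completely new events are captured in a trial that the protocol (2.1) describes as the first of its kind in chronic TMD, with 30 participants per arm. The safety sample in 12.3.1 is everyone who received at least one cycle, so an early leaver counts fully in the denominator while contributing less observation time. Section 12.4 plans only descriptive safety statistics and does not mention exposure or observation time.

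**Working it through.** **Inputs**
- Last injection for a completer: Visit 3, Day 56 (7.3.3).
- Last visit for a completer: Visit 5, Day 112 (7.4).
- End of recording: 30 days after participation ends (9.2).
- Interval between injections: 28 days (7.3.2, 7.3.3).

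**The plan's own figure.** Section 4 puts Visit 5 at 8 weeks after the last dose. 112 − 56 = 56 days = 8.0 weeks, so it reproduces.

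**Formula.** Post-dose window = (last day of participation − day of last dose) + 30.

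**Completer.** (112 − 56) + 30 = 86 days after the last dose. Recording ends on Day 112 + 30 = Day 142.

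**Participant leaving *w* days after a dose.** Window = *w* + 30; shortfall against a completer = 86 − (*w* + 30) = 56 − *w*.

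| *w* (days) | Window after that dose (days) | Shortfall (days) | Share of 86 |
|---|---|---|---|
| 0 | 30 | 56 | 35% |
| 7 | 37 | 49 | 43% |
| 14 | 44 | 42 | 51% |
| 28 | 58 | 28 | 67% |

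The range stops at 28 days because the next injection is then due. After the third injection a participant can leave later than that, and the window rises towards 86 days as the exit approaches Visit 5.

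**Sensitivity to the calendar.** Later pages of Appendix A use Days 30, 60, 90 and 120. On that grid a completer has (120 − 60) + 30 = 90 days, and a participant leaving 0 to 30 days after a dose has 30 to 60 days (33% to 67%). The conclusion does not change.

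**Scheduled enquiries about new events in the last 30 days:** none, for completers and early leavers alike.

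**The case against.** **Events behind a withdrawal are followed.** Sections 5.5.2 and 9.2 follow an event present at discontinuation until it settles, with referral if it has not settled within 30 days, and 9.4.2 does the same for serious events. A reader might infer that worsening constipation or blood pressure would be lost in participants withdrawn for those reactions. The documents do not support that. This stands, and it limits the gap to events that begin after the participant leaves.

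**Drug reactors are not singled out.** A reader might infer that participants withdrawn for reactions get the shortest follow-up. The same arithmetic applies to every early leaver, and those who withdraw consent and refuse the early termination visit have no further data collected (5.5.1). This also stands.

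**Bias against detecting harm is not shown.** A reader might infer that short windows fall mainly on the erenumab arm and hide its harms. Section 9.3.2 does say that injection site reactions and constipation were commoner than on placebo. But worsening TMD and starting a restricted therapy also end participation, and if erenumab works those exits would fall more on placebo. The net direction is open, and the reaction that triggers an exit is itself recorded.

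**The anchor alone is not at fault.** A window of 30 days from the last injection would cut completers from 86 to 30 days and end on Day 86, before Visit 5. The short window arises because leaving treatment means leaving the study. The documents also give no half-life or washout from which to derive an ideal length.

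**Procedures may exist elsewhere.** Appendix A lists no telephone calls at all, even those the text requires. Parts of 9.4.2 are redacted, and a Manual of Procedures is held separately. So the absence of a call from Appendix A is weak evidence by itself. However, 6.5 and 9.1 place calls between visits, and 7.4 and 7.5 leave later reporting to the participant.

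**Conclusion.** The point holds as a gap in active detection of new events. For every participant the last 30 days of recording contain no scheduled enquiry. Anyone leaving 0 to 28 days after a dose has a new-event window of 30 to 58 days after it, against 86 for a completer (35% to 67%). This assumes the 28-day calendar, that discontinuation ends participation on the same day, and that no separate procedure schedules a later call.

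The effect on the comparison between arms cannot be sized, because the documents give no rate of early withdrawal. The numbers leaving for any one reaction are likely to be small. Section 2.3.1 puts the identified reactions below 5% in trials, or fewer than 30 × 0.05 = 1.5 of 30 erenumab participants each. Section 9.3.2 gives 1 to 10 per 100, or 0.3 to 3 of 30. The case for change therefore rests on complete ascertainment at low cost, not on a demonstrated bias.

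**What to change.** - In 9.2, 7.4, 7.5 and Appendix A, schedule a telephone enquiry about new events at the end of the recording window for every dosed participant who has not withdrawn consent.
- In 9.2, for participants who leave early, continue recording new events over the post-dose interval completers already receive: 8 weeks plus 30 days, or 86 days, after the last injection. Someone leaving 0 to 28 days after a dose gains 56 to 28 days, and completers lose nothing. The 86 days is chosen for parity with completers, not derived from pharmacology.
- In 12.4, report adverse events by person-time as well as by counts.
- Reconcile the two 30-day clocks in 9.2 and the two day numberings for Visit 5 (Day 112 and Day 120), so that the end date is unambiguous.

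These changes concern data collection only and leave the withdrawal criteria as they are. The cost is one or two calls per participant, at most 60 to 120 calls for 60 participants, by staff who already telephone between visits, together with slightly longer data collection for early leavers.
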